3.1 Disposition and Exit Status

Participant disposition will be summarized as a frequency distribution by treatment groups. Participant disposition encompasses the distribution of participants who screened, randomized, complete, and discontinued, along with eCRF-reported discontinuation reasons.

3.2 Protocol Deviation

Protocol deviations will be captured and classified by categories in a separate document. Significant protocol deviations will be summarized for the mITT Population by treatment group.

3.3 Analysis Population

Number of participants included for mITT, PP and Safety population will be summarized for all participants in total and by treatment group. Listing of participants excluded from PP population will be provided with reasons for exclusions.

4. Demographics and Other Baseline Characteristics

4.1 Demographics

Demographic data including age, age group (<45, 45-65, >65), sex, and race will be summarized with descriptive statistics and frequency distribution in total and by treatment group.

700 µg DEX PS DDS

4.2 Baseline Characteristics

The following baseline characteristics will be summarized in total and by treatment group.

- Height (meters) and Weight (kilograms)
- Iris color (Blue, Green, Hazel, Brown, Other)
- Iris color groups, defined as Dark (brown, black, other which contains black in comments), Light (blue, green, hazel, other which doesn't contain black in comments)
- Duration of diabetic macular edema (DME) (months) in the study eye, calculated as (randomization date - DME onset date)/30.4
- BCVA score as a continuous variable and BCVA by randomization strata
- Central retinal thickness (CRT) (microns)
- Total area of macular leakage (mm²)
- lens status assessment: Phakic, Pseudophakic or Ahakic

4.3 Prior Medications

Prior medications include medications taken prior to the first study treatment. A medication or ophthalmic medication will be considered as a prior medication if it satisfies at least one of the following:

- The start date is prior to day 1, regardless of the stop date;
- The start date is unknown but marked as > 1 year; or
- The stop date is prior to or on day 1, regardless of the start date

For medications with a partial start or stop date where “> 1 year” is not marked for the start date or “ongoing” is not marked for the stop date and the day and/or the month is unknown, comparison to the study treatment date (Day 1) will start with the year followed by the month, if applicable, for determination of prior medications. In cases where a full determination cannot be made based on the partial information, the start date will be assigned to the 1st day of the month if the day of the month is missing or to January if the month of the year is missing; conversely, the stop date will be assigned to the last day of the month if the day of the month is missing or to December if the month is missing. This missing data imputation will be done for tabulation purposes. All partial dates will be listed as recorded in the medication listing.

Number and percentage of participants who reported prior medications will be summarized by Anatomical Therapeutic Chemical (ATC) 4 class and PT in total and by treatment group. ATC4 classes will be sorted alphabetically; PTs will be sorted in descending frequency in the

700 µg DEX PS DDS

highest dose group. A separate analysis for prior ophthalmic medications used in the study eye will be performed.

4.4 Concomitant Medications

Concomitant medications include medications taken after the first study treatment. A medication will be considered as a concomitant medication or concurrent procedure if it satisfies at least one of the following:

- The start date is on or after the Day 1 treatment date regardless of the stop date;
- The stop date is after the Day 1 treatment date, regardless of the start date; or
- The stop date is unknown but marked as ongoing

For medications with a partial start or stop date, the same conventions and algorithms as described for prior medications will be used for determination of concomitant medications

Medications and procedures will be coded the same way as prior medications. Concomitant medications will be summarized in the same way as that for prior medications. A separate summary for concomitant ophthalmic medications used in the study eye will be done.

Further, concurrent procedures will be summarized for each treatment group. Similarly, concurrent ocular procedures used for the study eye will be summarized for each treatment group.

4.5 Medical and Surgical History

Medical history including those ocular and non-ocular history, encompassing abnormalities and surgeries reported as occurring before the Screening Visit, will be coded using the Medical Dictionary for Regulatory Activities (MedDRA), version 19.1 or newer.

Number and percentage of participants who reported medical history events will be summarized by MedDRA system organ class (SOC) and preferred term (PT) in total and by treatment group for the mITT Population. SOCs will be sorted alphabetically; PTs will be sorted in descending frequency in the highest dose group. The similar summaries or listings will be done for the following events as appropriate:

- Medical history
- Medical conditions at the trial initiation
- Ophthalmic history in the study eye
- Ophthalmic condition in the study eye at trial initiation
- Surgical history

700 µg DEX PS DDS

- Ophthalmic surgical history in the study eye

5. Efficacy Analyses

Unless stated otherwise, analyses for efficacy will be performed using the mITT population for the study eye based on the 2-sided hypothesis test with a nominal significance level of 0.05.

5.1 Primary Efficacy Analyses

5.1.1 Collection of Primary Efficacy Measurements and Derivation of Primary Efficacy Variable

BCVA is measured using the Early Treatment Diabetic Retinopathy Study (ETDRS) method. The number of letters read correctly will be recorded.

The primary endpoint is the average change from baseline in BCVA in study eye over the 12-month study period for each participant. The average BCVA will be calculated as the area under the BCVA curve divided by the study days at the last BCVA measurement of the study eye over the 12-month study period.

Change from baseline = average BCVA – Baseline BCVA.

The area under the BCVA curve will be calculated using the trapezoidal method and will include all BCVA data, regardless of scheduled or unscheduled visits, from day 1 to the last BCVA assessment prior to escape therapy or at exit visit. The total area under the BCVA curve can be partitioned into sub-areas divided by consecutive visits that each participant had with BCVA measurements. For a particular participant, assume that BCVA is obtained at L

time points (visits) including the baseline visit. Let t_i and $BCVA_i$ represent the study day and BCVA value at Visit i (e.g., baseline/day 1, month 1, etc.), respectively, and

$t_i = t_1, t_2, \dots, t_L$, where $t_1 = \text{day 1 (baseline)}$ and,

$t_L = T$ (month 12 or time at the last BCVA if early term inated or at the 1st escape therapy)

The total area under the BCVA curve over $[1, T]$ study days:

$$AUC_{[1,T]} = \sum_{i=1}^{L-1} AUC_i(t_i, t_{i+1}), \text{ where } AUC_i = (BCVA_{t_{i+1}} + BCVA_{t_i}) * (t_{i+1} - t_i) / 2$$

The average BCVA for the participant = $\frac{1}{T-1} AUC_{[1,T]}$, and

The average BCVA change for the participant = $\frac{1}{T-1} AUC_{[1,T]} - BCVA_{\text{baseline}}$

5.1.2 Primary Efficacy Analysis

The primary analysis will be an analysis of covariance (ANCOVA) comparing the treatment difference in the mean average BCVA change from baseline over a 12-month study period. The ANCOVA model will include the treatment group as the main effect and baseline BCVA score as the covariate.

The null hypothesis is that there is no difference between 700-µg DEX PS DDS and laser in the average BCVA change from baseline in a 12-month period. The alternative hypothesis is that there exists a difference between the 2 treatment groups. The hypothesis test will be based on a 2-sided test at 0.05 significance level. In addition, a 2-sided 95% confidence interval (CI) will be constructed for the difference between the treatment groups in least-square means using the same ANCOVA model.

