Secondary Efficacy Analyses: Secondary efficacy analyses include a Cochran–Mantel-Haenszel (CMH) test stratified within each study site by baseline BCVA categories (≥ 34 to ≤ 49 and ≥ 50 to ≤ 70) for treatment difference in proportion of patients with ≥ 15 letters improvement from baseline of BCVA at month 12; and ANCOVA on retinal thickness and total leakage area at month 12.

700 µg DEX PS DDS

1. Background and Clinical Rationale

Diabetes affects more than 220 million people worldwide (World Health Organization, [WHO Diabetes Fact Sheet, 2011](#)) and its prevalence is expected to grow to 366 million by 2030 ([Wild et al, 2004](#)). Diabetic macular edema (DME) is 1 of the major causes of vision loss in patients with diabetic retinopathy ([Resnikoff et al, 2004](#)). Diabetic retinopathy (DR) and DME are common microvascular complications in patients with diabetes and may have sudden and debilitating impact on VA, eventually leading to blindness. DME is a frequent manifestation of DR and is a major cause of vision loss in patients with DR. DME results from retinal microvascular changes. Thickening of the basement membrane and reduction in the number of pericytes are believed to lead to increased permeability and incompetence of the retinal vasculature. This compromise of the blood-retinal barrier (BRB) leads to the leakage of plasma constituents into the surrounding retina, with subsequent retinal edema ([Albert and Jakobiec, 2000](#)). Increase of vascular permeability and breakdown of the BRB in DME is thought to be caused by vascular epithelial growth factor (VEGF) effects, such as phosphorylation of tight junctional protein occludin and Fas-mediated endothelial cell apoptosis, and also by inflammatory effects like leukostasis, possibly due to increased expression of leukocyte adhesion molecules ([Aiello et al, 1997](#)).

[figure not shown]

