5.5 Treatment Allocation Ratio and Stratification

Patients will be randomized in a 1:1 ratio to either 700 µg DEX PS DDS or laser photocoagulation.

The randomization will be stratified by BCVA score at baseline (≥ 34 to ≤ 49 and ≥ 50 to ≤ 70) within each study site.

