7.3.2 Secondary Efficacy Analyses

Analysis for proportion of patients with 15 or more letters improvement from baseline in BCVA at month 12 will be done using a Cochran–Mantel–Haenszel (CMH) test stratified by baseline BCVA categories (≥ 34 to ≤ 49 and ≥ 50 to ≤ 70) within each study site.

Analysis for change from baseline in retinal thickness at month 12 will be performed using an ANCOVA model with treatment and baseline BCVA score (≥ 34 to ≤ 49 and ≥ 50 to ≤ 70) as the main effects and baseline retinal thickness as the covariate. The between-group difference and the corresponding 2-sided 95% CI in least-square means will be computed using the ANCOVA model. The within-group change from baseline will be analyzed using the paired t-test at the follow-up visits.

Analysis for change from baseline in total leakage area at month 12 will be performed using an ANCOVA model with treatment and baseline BCVA score (≥ 34 to ≤ 49 and ≥ 50 to ≤ 70) as the main effects and baseline total leakage area as the covariate. The between-group difference and the corresponding 2-sided 95% CI in least-square means will be computed using the ANCOVA model. The within-group change from baseline will be analyzed using the paired t-test at the follow-up visits.

[REDACTED]

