1.1 Primary Study Objectives and Design

The objective of the study is to evaluate the safety and efficacy of 700µg DEX PS DDS administered every 5 months.

Consenting participants will participate in a screening period lasting 2 to 14 days to evaluate participant eligibility. After eligibility has been determined by the investigator, participants will be randomized in a 1:1 ratio to receive:

- 700 µg DEX PS DDS every 5 months
- or
- laser photocoagulation according to the modified ETDRS protocol

The randomization will be stratified by BCVA categories at baseline (≥ 34 to ≤ 49 and ≥ 50 to ≤ 70) within each investigator site. The primary efficacy variable is average change of BCVA over a period of 12 months. The total duration of study participation for each participant is approximately 12.5 months including screening and randomization/retreatment period. Participants will attend the following 11 visits: screening visit, randomization visit, 8 assessment/retreatment visits, and study exit visit, as listed in [Table 1-1](#).

2. Analysis Populations and Data Conventions

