5.2 Secondary Efficacy Analyses

Data after the 1st escape therapy will be set to missing. For participants who receive escape therapy or terminate early prior to month 12, month 12 data will be imputed using LOCF (Last Observation Carry Forward). The last observation prior to the 1st escape therapy or at early exit will be used for month 12. In the event of mis-randomization with an incorrect stratum, the actual stratum that the participant belongs will be used for statistical analysis.

5.2.1 BCVA Improvement of ≥ 15 Letters from Baseline at month 12

[figure not shown]
Analysis for proportion of participants with 15 or more letters improvement from baseline in BCVA of study eye at month 12 will be done using a Cochran–Mantel-Haenszel (CMH) test stratified by baseline BCVA categories (≥ 34 to ≤ 49 and ≥ 50 to ≤ 70). The 95% confidence intervals for the between-group difference in the proportion will be calculated using normal approximations.

5.2.2 Change from Baseline in Central Retinal Thickness at Month 12

Analysis for change from baseline in central retinal thickness measured by OCT at month 12 will be performed using an ANCOVA model with treatment and baseline BCVA category as the main effects and baseline retinal thickness as the covariate. The between-group difference and the corresponding 2-sided 95% CI in least-square means will be computed using the ANCOVA model.

5.2.3 Change from Baseline in Total Leakage Area at Month 12

The total area of macular leakage measured by FA is defined as the sum of focal and diffuse leakage area. Analysis for change from baseline in total leakage area at month 12 will be performed using an ANCOVA model with treatment and baseline BCVA categories as the main effects and baseline total leakage area as the covariate. The between-group difference and the corresponding 2-sided 95% CI in least-square means will be computed using the ANCOVA model.

6. Safety Analyses

The safety analysis will be based on safety population using observed data.

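### Randomisation is stratified by BCVA category within about 20 sites, but no visible efficacy ANCOVA includes site, and the SAP drops site from the protocol's 15-letter CMH test

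*SAP*

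**What the plan says.** **Randomisation.** Protocol 5.5 has allocation "stratified by BCVA score at baseline (≥ 34 to ≤ 49 and ≥ 50 to ≤ 70) within each study site". SAP 1.1 agrees: "The randomization will be stratified by BCVA categories at baseline", applied "within each investigator site". Protocol 4.1 and SAP 2.1 plan about 356 patients at about 20 sites.

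**Primary analysis.** SAP 5.1.2 states: "The ANCOVA model will include the treatment group as the main effect and baseline BCVA score as the covariate". Protocol 7.3.1 specifies the same terms.

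**Retinal thickness and leakage area.** For thickness, SAP 5.2.2 uses "treatment and baseline BCVA category as the main effects and baseline retinal thickness as the covariate". SAP 5.2.3 does the same for leakage, with baseline leakage as the covariate. Protocol 7.3.2 has the same terms for both. None of these models includes site.

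**15-letter responders at month 12.** The Protocol Summary describes a CMH "test stratified within each study site by baseline BCVA categories", and Protocol 7.3.2 has it "stratified by baseline BCVA categories (≥ 34 to ≤ 49 and ≥ 50 to ≤ 70) within each study site". SAP 5.2.1 stops at the category: "stratified by baseline BCVA categories (≥ 34 to ≤ 49 and ≥ 50 to ≤ 70). The 95% confidence intervals" are then said to rest on a normal approximation, without saying whether they use the strata.

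**The concern.** There are three separate matters.

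1. Balancing treatment within site removes site differences from the treatment comparison. A model without site still counts those differences as error. If outcomes vary by site, the standard error is too large and precision is lost. Some variation is plausible: Protocol 12.1.6 allows three OCT instruments, Protocol 5.7.2 leaves laser retreatment partly to the investigator's opinion, and SAP 1 places the trial in two countries.
2. The two documents name different tests for the same secondary endpoint. Investigators know the treatment assignment (Protocol 9.4), so which test counts should be settled before results are available. Otherwise a choice remains open between two tests that will sometimes disagree about significance.
3. The interval for the responder difference may not correspond to the test reported beside it.

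**Working it through.** **What can be reproduced.** The visible text gives no effect size, SD, power or dropout rate, so 151 completers per group cannot be rebuilt. The figures imply a loss of 1 − 302/356 = 15.2%; with 15%, 151/0.85 rounds up to 178 per group, or 356. No site variance is given, so the results below are ranges over assumed values.

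**ANCOVA, analytic.** Let r be the assumed share of residual variance due to site, with balance within site taken as perfect. The SE from the model without site is then too large by the factor k = 1/√(1 − r).

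- Type I error without site = 2[1 − Φ(1.96k)].
- Let λ = 1.96 + z(power), sized on the SE without site. Power without site = Φ((λ − 1.96)k); power with site = Φ(λk − 1.96).

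Example with r = 0.10: k = 1/√0.90 = 1.054. Type I error = 2[1 − Φ(2.066)] = 0.039. At an assumed 80%, λ = 1.96 + 0.842 = 2.802, so power is Φ(0.887) = 0.812 without site and Φ(0.993) = 0.840 with it.

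| r | SE too wide by | Type I error, no site | Power at 80%: no site / site | Power at 90%: no site / site |
|---|---|---|---|---|
| 0 | 0% | 0.050 | 0.800 / 0.800 | 0.900 / 0.900 |
| 0.02 | 1.0% | 0.048 | 0.802 / 0.808 | 0.902 / 0.906 |
| 0.05 | 2.6% | 0.044 | 0.806 / 0.820 | 0.906 / 0.914 |
| 0.10 | 5.4% | 0.039 | 0.812 / 0.840 | 0.912 / 0.927 |

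Power given up is 0/0.6/1.4/2.7 points at 80% and 0/0.3/0.8/1.6 points at 90%.

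**ANCOVA, simulated.** This allows for imperfect balance. Assumptions: 302 patients, 20 unequal sites, permuted blocks of 4 within site and category, 30% in the lower category; 8,000 null and 4,000 power runs.

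| r | Type I error: no site / site | Power: no site / site |
|---|---|---|
| 0 | 0.049 / 0.048 | 0.789 / 0.787 |
| 0.05 | 0.047 / 0.053 | 0.797 / 0.805 |
| 0.10 | 0.039 / 0.049 | 0.812 / 0.836 |
| 0.20 | 0.034 / 0.051 | 0.818 / 0.868 |

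The direction is the same. Adding site brings type I error back to about 0.05 and costs almost nothing when sites do not differ.

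**CMH test.** Twenty sites and two categories make about 40 strata, or 356/40 = 8.9 patients each, against 2 strata in the SAP. Assumptions: 4,000 trials per setting, 356 patients, 20 unequal sites, 35% in the lower category, blocks of 4, responders 22% v 11% (15% in both groups under the null), and pooling of sites with fewer than 16 patients.

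| Site SD (logit) | Power: 2 strata / 40 / pooled | Type I error: 2 strata / 40 / pooled | 2 v 40 disagree at 0.05: alternative / null | Patients in uninformative strata: 40 / pooled |
|---|---|---|---|---|
| 0 | 0.815 / 0.807 / 0.812 | 0.053 / 0.051 / 0.051 | 3.5% / 1.3% | 16% / 7% |
| 0.3 | 0.807 / 0.804 / 0.810 | 0.047 / 0.050 / 0.049 | 3.8% / 1.4% | 17% / 8% |
| 0.6 | 0.826 / 0.832 / 0.835 | 0.052 / 0.057 / 0.056 | 3.5% / 1.2% | 21% / 10% |
| 1.0 | 0.831 / 0.854 / 0.851 | 0.040 / 0.049 / 0.048 | 4.0% / 1.7% | 27% / 15% |

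Monte Carlo SE is about 0.6 points on power and 0.35 on type I error. Repeat simulations with similar assumed inputs gave disagreement of 3.1 to 5.4% under the alternative and 1.2 to 1.6% under the null.

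**Confidence interval.** If the interval ignored the strata, it would disagree with the 2-stratum test in only 0.5 to 0.7% of trials under the alternative.

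**The case against.** The primary model is identical in both documents, is conservative, and already adjusts for BCVA as a continuous score, which largely covers that part of the stratification. The gain from a site term depends on an assumed variance share and may be nil. Changing a model fixed in both documents is itself a departure from the protocol, in a trial where investigators know the assignment; a site-adjusted sensitivity analysis would be a milder response. On the CMH test, Protocol 7 defers detail to an analysis plan, so the SAP's version can be read as governing. The 40-stratum version is not consistently more powerful, and a pooled version appears in neither document. Redaction also matters: SAP section 9 is blacked out, no SAP section 7 is visible, text after Protocol 7.3.2 is hidden, and the SAP references a small-sample mixed-model method with no visible use.

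Much of this stands. The site term is a gain in precision, not the repair of an error. The interval question is one of wording. It cannot be said that no explanation exists, only that none is visible. The CMH conflict remains all the same: SAP 1 presents itself as specifying the analyses set out in the amended protocol, its amendments section is empty, and two tests are on record for one endpoint. Any explanation in hidden text would leave SAP 5.2.1 and Protocol 7.3.2 to be reconciled.

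**Conclusion.** The concern holds, at modest size. No visible ANCOVA includes site, although site is part of the stratification. For an assumed site share of 0 to 10%, this costs 0 to 2.7 points of power at an assumed 80%, or 0 to 1.6 at 90%, and keeps type I error at or below its nominal level. It does not weaken a positive superiority result. Small or incomplete blocks would reduce both the balance and the conservatism.

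The stronger ground for action is the mismatch in the responder test. Under the assumed site sizes, block size and response rates, the two versions reach opposite conclusions in 3.5 to 4.0% of trials under the alternative and 1.2 to 1.7% under the null. Neither is clearly the better test; what matters is that one is fixed in advance. The changes should be made because they are cheap.

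**What to change.** Before database lock:

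1. Add site to the primary, thickness and leakage ANCOVAs, pooling small sites by a rule fixed in advance, and record this as a change from Protocol 7.3.1 and 7.3.2.
2. State one CMH stratification for both documents. The default is the protocol's BCVA category within site, under the same pooling rule. The alternative is to keep BCVA category only and document the reason.
3. State that the interval for the responder difference is Mantel-Haenszel weighted over the same strata as the CMH test.

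This needs SAP wording and a documented protocol departure, but no new data. The ANCOVA loses about 19 degrees of freedom: with 356 patients analysed, 356 − 3 = 353 residual falls to 334, which is negligible. A pooling rule has to be written, and in the CMH test some 7 to 15% of patients would still sit in uninformative strata after pooling (simulated, under the stated assumptions).

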5.1.3 Other Analyses of Primary Efficacy Variable

As a supportive analysis, the above analyses will be done using PP population.

5.2 Secondary Efficacy Analyses

Data after the 1st escape therapy will be set to missing. For participants who receive escape therapy or terminate early prior to month 12, month 12 data will be imputed using LOCF (Last Observation Carry Forward). The last observation prior to the 1st escape therapy or at early exit will be used for month 12. In the event of mis-randomization with an incorrect stratum, the actual stratum that the participant belongs will be used for statistical analysis.

5.2.1 BCVA Improvement of ≥ 15 Letters from Baseline at month 12

[figure not shown]
Analysis for proportion of participants with 15 or more letters improvement from baseline in BCVA of study eye at month 12 will be done using a Cochran–Mantel-Haenszel (CMH) test stratified by baseline BCVA categories (≥ 34 to ≤ 49 and ≥ 50 to ≤ 70). The 95% confidence intervals for the between-group difference in the proportion will be calculated using normal approximations.

5.2.2 Change from Baseline in Central Retinal Thickness at Month 12

Analysis for change from baseline in central retinal thickness measured by OCT at month 12 will be performed using an ANCOVA model with treatment and baseline BCVA category as the main effects and baseline retinal thickness as the covariate. The between-group difference and the corresponding 2-sided 95% CI in least-square means will be computed using the ANCOVA model.

5.2.3 Change from Baseline in Total Leakage Area at Month 12

The total area of macular leakage measured by FA is defined as the sum of focal and diffuse leakage area. Analysis for change from baseline in total leakage area at month 12 will be performed using an ANCOVA model with treatment and baseline BCVA categories as the main effects and baseline total leakage area as the covariate. The between-group difference and the corresponding 2-sided 95% CI in least-square means will be computed using the ANCOVA model.

6. Safety Analyses

The safety analysis will be based on safety population using observed data.

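### SAP 5.2.1 does not say how the 95% CI for the 15-letter difference is built; read plainly it is an unstratified Wald interval set beside a stratified CMH test

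*SAP*

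**What the plan says.** SAP 5.2.1 analyses the month-12 proportion with a gain of 15 letters or more by a CMH "test stratified by baseline BCVA categories (≥ 34 to ≤ 49 and ≥ 50 to ≤ 70"). The next sentence reads: "The 95% confidence intervals for the between-group difference in the proportion will be calculated using normal approximations". Nothing more is said about the estimator, its weights or its variance.

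The neighbouring endpoints are handled differently. For retinal thickness and leakage area (SAP 5.2.2 and 5.2.3) the "2-sided 95% CI in least-square means will be computed using the ANCOVA model", and SAP 5.1.2 takes the primary interval from the same ANCOVA as the primary test. The 15-letter endpoint is therefore the only primary or secondary endpoint whose interval is not tied to its comparison.

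On design, SAP 1.1 states: "The randomization will be stratified by BCVA categories at baseline", within site and in a 1:1 ratio. Protocol 7.3.2 names no interval for this endpoint. It describes the CMH test as "stratified by baseline BCVA categories (≥ 34 to ≤ 49 and ≥ 50 to ≤ 70) within each study site", whereas the SAP uses BCVA category alone.

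**The concern.** The p-value conditions on baseline BCVA category. An unstratified interval does not. The chance of a 15-letter gain plausibly depends on starting vision. If it does, the unstratified standard error contains between-category variation that the stratified test removes, so the interval is wider than it need be. A report could then show CMH p below 0.05 beside an interval that includes zero.

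The text also leaves a choice open. A Mantel-Haenszel risk difference with a Wald-type interval is a normal approximation too, so two programmers could follow the sentence and produce different intervals. That choice should be settled before database lock.

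**Working it through.** **Inputs from the documents.** Two-sided 0.05 (opening of SAP Section 5); 1:1 allocation; about 356 enrolled, so 178 per arm; at least 151 completers per arm (SAP 2.1). SAP 5.2 carries the last observation forward to month 12, so the denominators should lie nearer 178 than 151.

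**Plan's own figure.** None exists for this endpoint: no rate, power or interval width is visible. The one related figure is consistent: 2 × 151 = 302, and 302/0.85 = 355.3, rounded up to 356. The 15% loss is back-solved, not stated.

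**Assumed.** Response rates by category, and about 35% of patients in the lower category (62 of 178 per arm).

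**Why the unstratified variance is larger.** Within an arm, with category shares π_k, rates p_k and overall rate p:

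p(1−p) = Σπ_k p_k(1−p_k) + Σπ_k(p_k−p)²

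The last term enters the unstratified variance but not the stratified one.

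**Worked example.** This was chosen to show that a contradiction is possible; it is not a typical trial. There are 178 per arm, with categories of 62 and 116 in each. Responders: implant 34 + 6 = 40, laser 24 + 2 = 26.

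- CMH: observed minus expected = 40 − (29 + 4) = 7. Variance = 7.7805 + 1.9394 = 9.7199. Chi-square = 49/9.7199 = 5.04, p = 0.025.
- Unstratified: difference = 14/178 = 7.9 points. SE = √[(0.2247×0.7753 + 0.1461×0.8539)/178] = 0.0410. CI −0.2 to 15.9 points.
- Stratified, Mantel-Haenszel weights 62/178 and 116/178: difference again 14/178 = 7.9 points. SE = 0.0345 (weighted Wald), CI 1.1 to 14.6; SE = 0.0348 (Sato), CI 1.0 to 14.7.

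The arms are balanced and the estimates identical, so the contradiction comes from the variance alone. The implant arm's 0.1742 splits into 0.1182 within and 0.0560 between categories; the laser arm's 0.1247 splits into 0.0937 and 0.0311 (rounded).

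**How often.** 200,000 simulated trials per row, 62 + 116 per arm, same counts in both arms. Rates are lower/upper BCVA category.

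| Implant v laser (assumed) | Unstratified SE ÷ weighted Wald SE (÷ Sato SE) | Unstratified coverage | CMH rejects, unstratified CI includes 0 | Sato CI disagrees with CMH |
|---|---|---|---|---|
| 26.2/26.2% v 16.5/16.5% | 1.003 (1.000) | 94.9% | 0.0% | 0.4% |
| 32/16% v 20/8% | 1.020 (1.016) | 95.3% | 0.6% | 0.5% |
| 30/6% v 15/2% | 1.054 (1.041) | 95.9% | 2.2% | 0.4% |
| 40/12% v 25/5% | 1.057 (1.050) | 96.0% | 2.8% | 0.4% |
| 40/10% v 25/5% | 1.065 (1.055) | 96.2% | 3.6% | 0.5% |
| 55/10% v 40/5% | 1.139 (1.129) | 97.3% | 9.3% | 0.5% |

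The first row borrows the month-4 vision-improvement rates of the earlier DME study in Protocol Section 1, as illustration only. There the only disagreement is the reverse one (interval excludes zero, CMH does not reject), at 0.7%. With 53 + 98 = 151 per arm, the three moderate rows (third to fifth) give 2.7%, 3.1% and 3.8%. Sato coverage in those rows is 94.9% to 95.1% at either size.

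A second simulation let category counts differ between arms by up to 4 patients and counted disagreement in both directions. With a true effect, the unstratified interval disagreed with CMH in 0.6% to 1.4% of trials when categories had equal rates. The figures were 2.2% to 3.6% at laser rates of 20%/8%, 3.8% to 6.6% at 25%/5%, and 8.4% to 11.4% at 40%/5%. Stratified intervals (Sato or weighted Wald) disagreed in 0.4% to 1.1%.

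**The case against.** A reader might infer that the SAP prescribes a crude interval that ignores the strata. It does not say so. The wording also covers a stratum-weighted difference, the sentence directly follows the one naming the stratified test, and SAP Section 1 places table specifications in a separate document not available here. This stands: what the text supports is under-specification, and the unstratified interval is only its plain reading.

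A reader might also infer that an unstratified interval would be invalid or biased. Under 1:1 randomisation stratified by BCVA category, the unstratified difference is a sound estimate of the overall effect. Coverage stayed between about 95% and 97% in every scenario tabulated, so the error is on the cautious side. An imbalance such as 65 against 54 lower-category patients of 178 would move it by (11/178) × 15 to 20 points, or 0.9 to 1.2 points. Nothing in the documents makes a gap of that size likely, and in the second simulation the two point estimates differed by only 0.04 to 0.95 points on average.

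The impact depends on assumed prognostic differences, and the endpoint is secondary, tested at a nominal level. That also stands and limits the weight of the point. What remains is that the text permits more than one interval, and that its plain reading forgoes precision from a factor on which the trial already stratifies.

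**Conclusion.** The point holds as a small improvement in specification and precision. SAP 5.2.1 leaves the interval for the 15-letter difference undefined, and the plain reading does not match the stratified test beside it.

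Under moderate assumed differences between BCVA categories, that reading costs about 5% to 6% in standard error (5.4% to 6.5% against the weighted Wald SE, 4.1% to 5.5% against Sato). Coverage is about 96%, and roughly 2% to 4% of trials have CMH rejecting while the interval includes zero. Steeper assumed differences raise this to about 9% or more; equal rates bring it to almost nothing. All of these sizes rest on assumed rates and category shares.

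The CMH test, the primary analysis and the trial's main conclusion are untouched. The documents do not support saying that the planned interval is wrong, or that it would usually contradict the test.

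**What to change.** In SAP 5.2.1 replace the sentence on the interval with: *The between-group difference will be estimated as the Mantel-Haenszel weighted risk difference across the baseline BCVA categories used in the CMH test, with a 95% CI based on the Sato variance.* Keep the unadjusted percentages as descriptive results.

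Settle the CMH strata in the same edit, since Protocol 7.3.2 stratifies within site and the SAP does not. If site is kept, about 20 sites × 2 categories gives 40 strata of roughly 356/40 = 9 patients. The Sato variance tolerates such sparse strata; a weighted Wald variance is less safe there.

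The cost is one sentence before database lock and a routine calculation. Some disagreement between test and interval will remain, about 0.4% to 1.1% of simulated trials with a true effect, because the two use different variances. If the categories respond alike, the gain is little or none.
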